**Figure 4. Adverse Event Collection**

\* Subjects who discontinue study drug treatment but continue to participate in the study will have SAEs and Nonserious AEs collected for the remainder of study participation.

Additionally, in order to assist the adjudication process, additional information on any potential cardiovascular events including thromboembolic events will be collected, if applicable.

In case of any of the following reported events, an appropriate supplemental eCRF should be completed:

- Cardiac events;
- Myocardial infarction or unstable angina;
- Heart failure;
- Cerebral vascular accident and transient ischemic attack;
- Cardiovascular procedures (SAE Supplemental Procedure eCRF);
- Embolic and thrombotic events (non-cardiac, non-CNS);
- Hepatic;
- Renal;
- Herpes Zoster Infection;
- CPK increases considered by the investigator to be an AE;
- COVID-19

Supplemental study case report forms should be completed in the event of COVID-19 related missed/virtual visits, study drug interruptions or discontinuations, or adverse events (including documentation of specific signs/symptoms of infection and testing results).

COVID-19 infections should be captured as adverse events. If the event meets the criteria for a serious adverse event (SAE), then follow the SAE reporting directions per the protocol and above.

The following COVID-19 related supplemental eCRFs should be completed (for both serious and non-serious events):

- COVID -19 Supplemental Signs/ Symptoms

- COVID-19 Status Form

**[contact]**

The sponsor will be responsible for Suspected Unexpected Serious Adverse Reactions (SUSAR) reporting for the Investigational Medicinal Product (IMP) in accordance with Global and Local Regulations. The reference document used for SUSAR reporting in the European Union countries will be the most current version of the Investigator's Brochure.

#### **6.1.6 Pregnancy**

Pregnancy in a study subject must be reported to AbbVie within 24 hours after the site becomes aware of the pregnancy. Subjects who become pregnant during the study must be discontinued from study drug (Section 5.4.1).

Information regarding a pregnancy occurrence in a study subject or the partner of an enrolled subject and the outcome of the pregnancy will be collected. Pregnancies in study subjects and their partners will be identified from the date of the first dose through 30 days following the last dose of study drug and the pregnancy will be followed to outcome.

Pregnancy in a study subject is not considered an AE. However, the medical outcome of an elective or spontaneous abortion, stillbirth, or congenital anomaly is considered an SAE and must be reported to AbbVie within 24 hours of the site becoming aware of the event.

Subjects should avoid pregnancy throughout the course of the study, starting with the Screening Visit through 30 days after the last study drug administration. Results of a positive pregnancy test or confirmation of a pregnancy will be assessed starting with the Screening Visit through the final study visit.

### **6.1.7 Toxicity Management**

The toxicity management of the AEs including AEs of special interest consists of safety monitoring (review of AEs on an ongoing basis, and periodical/ad hoc review of safety issues by a safety data monitoring committee), interruption of study drug dosing with appropriate clinical management if applicable, and discontinuation of the subjects from study drug. The management of specific AEs and laboratory parameters is described below.

For subjects who discontinued study drug but continued study participation and are on standard of care therapies, these toxicity management requirements do not apply (including alerts from the central lab) and any intolerability to standard of care therapies should be managed by the prescribing physician.

**Serious Infections:** Subjects should be closely monitored for the development of signs and symptoms of infection during and after treatment with study drug. Study drug should be interrupted if a subject develops a serious infection or an opportunistic infection. A

subject who develops a new infection during treatment with study drug should undergo prompt diagnostic testing appropriate for an immunocompromised subject. As appropriate, antimicrobial therapy should be initiated, and the subject should be closely monitored. Re-challenge with study drug may occur once the infection has been successfully treated. Subjects who develop active TB must be discontinued from study drug.

**COVID-19:** Interrupt study drug in subjects with a confirmed diagnosis of COVID-19. Consider interrupting study drug in subjects with signs and/or symptoms and suspicion of COVID-19. The COVID-19 eCRF must be completed.

**Herpes Zoster:** If a subject develops herpes zoster, consider temporarily interrupting study drug until the episode resolves.

**Gastrointestinal Perforation:** If a diagnosis of gastrointestinal perforation is confirmed (other than appendicitis or penetrating injury), the subject must be permanently discontinued from study drug.

**Cardiovascular Events (MACE):** Subjects presenting with potential cardiovascular events should be carefully monitored. These events will be reviewed and adjudicated by an independent Cardiovascular Adjudication Committee in a blinded manner.

**Thrombosis Events:** Subjects who develop symptoms of thrombosis should be promptly evaluated and treated appropriately. If the diagnosis of deep vein thrombosis, pulmonary embolus or non-cardiac, non-neurologic arterial thrombosis is confirmed, the subject must be discontinued from study drug.

**Malignancy:** Subjects who develop malignancy other than NMSC or carcinoma in situ of the cervix must be discontinued from study drug. Information including histopathological results should be queried for the confirmation of the diagnosis. Periodic skin examination is recommended for subjects who are at increased risk for skin cancer.

**ECG Abnormality:** Subjects must be discontinued from study drug for an ECG change considered clinically significant and with reasonable possibility of relationship to study drug OR a confirmed absolute QTcF value > 500 msec.

**Management of Select Laboratory Abnormalities:** For any given laboratory abnormality, the Investigator should assess the subject, apply the standard of care for medical evaluation and treatment following any local guidelines. Specific toxicity management guidelines for abnormal laboratory values are described in [Table 4](#), and may require an appropriate supplemental eCRF to be completed. All abnormal laboratory tests that are considered clinically significant by the Investigator will be followed to a satisfactory resolution. If a repeat test is required per [Table 4](#), the repeat testing must occur as soon as possible.

**Table 4. Specific Toxicity Management Guidelines for Abnormal Laboratory Values**

Laboratory Parameter	Toxicity Management Guideline
Hemoglobin	
 
• If hemoglobin < 8 g/dL interrupt study drug dosing and confirm by repeat testing with a new sample
 
• If hemoglobin decreases <math>\geq 3.0</math> g/dL from baseline without an alternative etiology, interrupt study drug dosing and confirm by repeat testing with new sample.
 
• If hemoglobin decreases <math>\geq 3.0</math> g/dL from baseline and an alternative etiology is known, the subject may remain on study drug at the investigator's discretion.
 
• If confirmed, continue to withhold study drug until hemoglobin value returns to normal reference range or its baseline value.
 

Absolute neutrophil count (ANC)	
 
• If confirmed < 1000 cells/<math>\mu</math>L by repeat testing with new sample, interrupt study drug dosing until ANC value returns to normal reference range or its baseline value.
 
• Discontinue study drug if confirmed < 500 cells/<math>\mu</math>L by repeat testing with new sample.
 

Absolute lymphocyte counts (ALC)	
 
• If confirmed < 500 cells/<math>\mu</math>L by repeat testing with new sample, interrupt study drug dosing until ALC returns to normal reference range or its baseline value.
 

Total white blood cell count	
 
• If confirmed < 2000 cells/<math>\mu</math>L by repeat testing with new sample, interrupt study drug dosing until white blood cell count returns to normal reference range or its baseline value.
 

**Table 4. Specific Toxicity Management Guidelines for Abnormal Laboratory Values (Continued)**

Laboratory Parameter	Toxicity Management Guideline
Platelet count	
 
• If confirmed <math>< 50,000</math> cells/<math>\mu</math>L by repeat testing with new sample, interrupt study drug dosing until platelet count returns to normal reference range or its baseline value.
 

AST or ALT	
 
• Interrupt study drug immediately if confirmed ALT or AST <math>> 3 \times</math> ULN by repeat testing with new sample and either a total bilirubin <math>> 2 \times</math> ULN or an international normalized ratio <math>> 1.5</math>.               
 
○ A separate blood sample for INR testing will be needed to measure INR at the time of repeat testing for ALT or AST. A repeat test of INR is not needed for determination if above toxicity management criteria are met.
 
 
 
• Interrupt study drug immediately if confirmed ALT or AST <math>> 3 \times</math> ULN by repeat testing with new sample along with appearance of fatigue, nausea, vomiting, right upper quadrant pain or tenderness, fever, rash, and/or eosinophilia (<math>> 5\%</math>).
 
• Interrupt study drug immediately if confirmed ALT or AST <math>> 5 \times</math> ULN by repeat testing with new sample for more than 2 weeks.
 
• If ALT or AST <math>> 8 \times</math> ULN, interrupt study drug immediately, confirm by repeat testing with a new sample and contact the TA MD.
 
 
Subjects who meet any of the above criteria should be evaluated for an alternative etiology of the ALT or AST elevation and managed as medically appropriate. If applicable, the alternative etiology should be documented in the eCRF. If ALT or AST values return to the normal reference range or its Baseline value, study drug may be restarted. If restarting study drug, documentation should include reason that rechallenge is expected to be safe. If after clinically appropriate evaluation, no alternative etiology for ALT or AST elevation is found or the ALT or AST elevation has not resolved or is not trending down toward normal, the subject should be discontinued from study drug. For any confirmed ALT or AST elevations <math>> 3</math> ULN, complete supplemental hepatic eCRF.
 
 
• Subjects with HBc Ab+ (irrespective of HBs Ab status) and negative HBV DNA at screening who develop the following should have HBV DNA by PCR testing performed within 1 week:               
 
○ ALT <math>> 5 \times</math> ULN OR
 
○ ALT or AST <math>> 3 \times</math> ULN if an alternative cause is not readily identified.
 
 
 
 
A positive result for HBV DNA PCR testing in these subjects will require immediate interruption of study drug and a hepatologist consultation should occur within 1 week for recommendation regarding subsequent treatment.


**Table 4. Specific Toxicity Management Guidelines for Abnormal Laboratory Values (Continued)**

Laboratory Parameter	Toxicity Management Guideline
Serum Creatinine	
 
If serum creatinine is <math>> 1.5 \times</math> the baseline value and <math>> \text{ULN}</math>, repeat the test for serum creatinine (with subject in an euvoletic state) to confirm the results. If the results of the repeat testing still meet this criterion then interrupt study drug and re-start study drug once serum creatinine returns to <math>\leq 1.5 \times</math> baseline value and <math>\leq \text{ULN}</math>.
 
If confirmed serum creatinine <math>\geq 2 \text{ mg/dL}</math>, interrupt study drug and re-start study drug once serum creatinine returns to normal reference range or its baseline value.
 
 
For the above serum creatinine elevation scenarios, complete supplemental renal eCRF.

Creatine Phosphokinase	
 
If confirmed CPK <math>\geq 4 \times \text{ULN}</math>, and there are no symptoms suggestive of myositis or rhabdomyolysis subjects may continue study drug at the investigator's discretion.
 
If CPK <math>\geq 4 \times \text{ULN}</math> accompanied by symptoms suggestive of myositis or rhabdomyolysis, interrupt study drug and inform AbbVie Therapeutic Area Medical Director.
 
 
For the above CPK elevation scenarios, complete supplemental CPK eCRF.

For allowed study drug interruption, the following rules apply:

#### Period 1

- Allow study drug interruption up to 7 consecutive days for AEs and emergency surgery. Elective surgery will not be allowed during this 24-week period.
- If the subject must undergo emergency surgery, the study drug should be interrupted at the time of the surgery. After emergency surgery, allow reintroduction of study drug once the physician has examined the surgical site and determined that it has healed and there is no sign of infection.

#### Period 2

- Allow study drug interruption up to 30 consecutive days. The Investigator will make determination if study drug should be restarted for interruptions  $> 30$  days.
- If the subject undergoes elective surgery, the study drug should be interrupted 1 week prior to the planned surgery. Allow reintroduction of study drug once

the physician has examined the surgical site and determined that it has healed and there is no sign of infection.

- If the subject must undergo emergency surgery, the study drug should be interrupted at the time of surgery. Allow reintroduction of study drug once the physician has examined the surgical site and determined that it has healed and there is no sign of infection.

Additional local requirements may apply. Refer to [Appendix C](#) for local requirements for France.

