  9. Systemic use of known strong cytochrome P450 (CYP)3A inhibitors or strong CYP3A inducers from Screening through the end of the study (refer to Table 1 for examples of commonly used strong CYP3A inhibitors and inducers).
  10. Receipt of any live vaccine within 4 weeks prior to the first dose of study drug, or expected need of live vaccination during study participation including at least 4 weeks after the last dose of study drug.
  11. History of any malignancy except for successfully treated NMSC or localized carcinoma in situ of the cervix.
  12. History of clinically significant (per Investigator's judgment) drug or alcohol abuse within the last 6 months.
  13. History of gastrointestinal perforation (other than appendicitis or penetrating injury), diverticulitis or significantly increased risk for GI perforation per investigator judgment.
  14. Conditions that could interfere with drug absorption including but not limited to short bowel syndrome.
  15. Subject has been a previous recipient of an organ transplant.
  16. History of clinically significant medical conditions or any other reason that in the opinion of the Investigator would interfere with the subject's participation in this study or would make the subject an unsuitable candidate to receive study drug.
  17. Active infection(s) requiring treatment with parenteral anti-infectives within 30 days, or oral anti-infectives within 14 days prior the first dose of study drug.

18. History of an allergic reaction or significant sensitivity to constituents of the study drug (and its excipients) and/or other products in the same class.
19. Laboratory values meeting the following criteria within the Screening period prior to the first dose of study drug:
  - Serum aspartate transaminase (AST)  $> 2 \times$  ULN;
  - Serum alanine transaminase (ALT)  $> 2 \times$  ULN;
  - Estimated glomerular filtration rate (GFR) by simplified 4-variable Modification of Diet in Renal Disease (MDRD) formula  $< 40$  mL/min/1.73 m^2;
  - Total white blood cell (WBC) count  $< 2,500/\mu\text{L}$ ;
  - Absolute neutrophil count (ANC)  $< 1,500/\mu\text{L}$ ;
  - Platelet count  $< 100,000/\mu\text{L}$ ;
  - Absolute lymphocyte count  $< 800/\mu\text{L}$ ;
  - Hemoglobin  $< 10$  g/dL.
20. History of any of the following cardiovascular conditions:
  - Moderate to severe congestive heart failure (New York Heart Association class III or IV);

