#### **8.1.5.3 Analysis of Laboratory, Vital Sign, and ECG Data**

Changes from baseline by visit, and changes from baseline to minimum value, maximum value, and final values in continuous laboratory data, and vital signs will be summarized by treatment group.

Baseline values are defined as the last non-missing measurements recorded on or before the date of the first dose of study drug in Period 1.

The laboratory data will be categorized as Grade 1, Grade 2, Grade 3, and Grade 4 according to OMERACT criteria (Rheumatology Common Toxicity Criteria v.2.0). For creatine phosphokinase and serum creatinine, NCI CTC criteria will be used. The shift tables will tabulate the number and percentage of subjects with baseline and post-baseline values by grade level.

Listings will be provided for potentially clinically significant laboratory values and vital signs.

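### The two serum-creatinine bullets in Table 4 (and France Table 5) can both apply to one subject, yet they set different restart conditions with no stated precedence, most sharply when baseline is above ULN

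*Protocol*

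**What the plan says.** Protocol Section 6.1.7, Table 4, has two bullets in the serum creatinine row.

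- **First bullet (relative rise).** The trigger is a value above 1.5 × baseline and above ULN. The site must "repeat the test for serum creatinine (with subject in an euvoletic state) to confirm the results". Then: "If the results of the repeat testing still meet this criterion then interrupt study drug and re-start study drug once serum creatinine returns to" a level that is both at or below 1.5 × baseline and at or below ULN.
- **Second bullet (absolute level).** The trigger is a confirmed value of 2 mg/dL or more. The instruction is to "interrupt study drug and re-start study drug once serum creatinine returns to normal reference range or its baseline value".

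Neither bullet refers to the other. France has its own table (Appendix C, Table 5), which repeats the pair with the same limits.

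Three other places bear on the point.

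- **Entry.** Section 5.2.2, criterion 19, excludes subjects by "Laboratory values meeting the following criteria within the Screening period prior to the first dose of study drug". The one renal item is "Estimated glomerular filtration rate (GFR) by simplified 4-variable Modification of Diet in Renal Disease (MDRD) formula" below 40 mL/min/1.73 m². The list has no creatinine limit.
- **Baseline.** For laboratory analyses, Section 8.1.5.3 states: "Baseline values are defined as the last non-missing measurements recorded on or before the date of the first dose of study drug".
- **Long interruptions.** The rules after Table 4 say for Period 2: "The Investigator will make determination if study drug should be restarted for interruptions" of more than 30 days. Section 5.5.4 gives the Investigator the same decision after more than 7 consecutive days in Period 1 or more than 30 in Period 2.

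**The concern.** A subject whose creatinine reaches 2 mg/dL will usually be under both bullets at once. If the bullets disagree on when to restart, two sites can treat identical subjects differently and both be following the protocol.

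The sharpest case is a baseline above ULN. The protocol lets such a subject take the first dose at that creatinine. After an interruption, the first bullet still withholds drug at the same creatinine, while the second says to restart. Every other Table 4 row that states a restart level (hemoglobin, ANC, ALC, WBC, platelets, AST/ALT) accepts return to baseline. The first creatinine bullet alone does not.

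Increased serum creatinine and renal dysfunction is an adverse event of special interest (Section 6.1.1.3). Uneven restarts would alter how long subjects are actually on drug. They could also alter the Period 2 discontinuation summaries (SAP Section 7.0) and the long-term exposure and event-rate analyses (SAP Sections 8.1 and 10.2.2).

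**Working it through.** The plan states no figure to reproduce; the check is of the logic of the two bullets. Let B be baseline, U the ULN and S the current creatinine, all in mg/dL. U is not given in the documents. I assume 0.9 to 1.4, with 1.2 for the worked cases.

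**Step 1: when both triggers fire.** The first needs S > 1.5B and S > U; the second needs S ≥ 2. If 1.5B < 2, that is B < 2/1.5 = 1.33, then every S ≥ 2 exceeds 1.5B. It also exceeds U whenever U < 2. So below a baseline of 1.33, any value that fires the second bullet fires the first. Above 1.33 there is a gap: with B = 1.5, 1.5B = 2.25, so S = 2.1 fires only the second bullet and S = 2.4 fires both.

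**Step 2: the restart ceilings.**

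- First bullet: S ≤ 1.5B and S ≤ U, so the ceiling is min(1.5B, U).
- Second bullet: S within normal range or back to B, so the ceiling is max(B, U), setting aside values below the lower limit of normal.

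The first ceiling is never above the second. They compare as follows.

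- B < U/1.5: 1.5B against U. They differ.
- B from U/1.5 to U: U against U. They agree.
- B > U: U against B. They differ.

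Over the assumed range of U, U/1.5 runs from 0.60 to 0.93.

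**Step 3: worked cases, U = 1.2.**

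| B | Peak (both fire) | First ceiling | Second ceiling | Later S | First bullet | Second bullet |
|---|---|---|---|---|---|---|
| 0.6 | 2.1 | min(0.9, 1.2) = 0.9 | max(0.6, 1.2) = 1.2 | 1.1 | withhold | restart |
| 0.9 | 2.1 | min(1.35, 1.2) = 1.2 | max(0.9, 1.2) = 1.2 | 1.2 | restart | restart |
| 1.3 | 2.1 | min(1.95, 1.2) = 1.2 | max(1.3, 1.2) = 1.3 | 1.3 | withhold | restart |
| 1.5 | 2.4 | min(2.25, 1.2) = 1.2 | max(1.5, 1.2) = 1.5 | 1.5 | withhold | restart |

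**Step 4: grid check.** Baselines ran from 0.40 to 2.00 and S up to 6.00, in steps of 0.05, with U at 0.9, 1.0, 1.1, 1.2, 1.3 and 1.4. Some S fired both bullets at every baseline. The second bullet cleared while the first withheld at 174 to 269 grid points per U. The reverse occurred at none.

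**Step 5: the first bullet alone.** With U = 1.2 and B = 1.25, 1.5B = 1.875. A confirmed 1.9 fires only the first bullet. Return to 1.25 does not meet its restart condition, because 1.25 > 1.2. So for a baseline above ULN the first bullet does not recognise return to baseline, whether or not the second has fired.

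**Step 6: can baseline exceed ULN at entry?** Criterion 19 does not bar it. As an illustration only, assume MDRD coefficients, which the protocol does not print: for a man aged 55 at 1.5 mg/dL, 175 × 1.5^(-1.154) × 55^(-0.203) = 48.6 mL/min/1.73 m². With a constant of 186 instead, it is about 52. Both are above the limit of 40.

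**The case against.** Several arguments on the other side have force.

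- **The conditions are nested.** A reader might infer that the bullets are incompatible. They are not: a non-low value that meets the first restart condition always meets the second. Two holds can be read as cumulative, so that the stricter controls. That is a sensible default, but the text does not state it. Under it, a subject with baseline above ULN stays off drug at the creatinine at which dosing was allowed to begin.
- **The bar need not last.** A reader might infer that such a subject is barred permanently. The documents do not support that. The first bullet clears once creatinine falls to ULN or below, and the Investigator has a restart decision after long interruptions. Section 6.1.7 also calls the table guidelines. However, neither Section 5.5.4 nor the text after Table 4 says whether the Investigator's decision overrides the table, so it is one more instruction to reconcile.
- **A gap between stopping and restarting is not an error.** A reader might fault the first bullet because a value that no longer fires it can still block restart. The ANC, ALC, WBC and platelet rows share that feature, so I make nothing of it. What sets the first bullet apart is the missing baseline alternative.
- **Other entry safeguards exist.** Section 5.3.1.1 (Randomization/Drug Assignment) bars enrolment for clinically significant screening abnormalities, and criterion 16 leaves room for judgment. They narrow the above-ULN group without closing it.
- **Week 12 results are untouched.** A reader might infer an effect on non-responder status. SAP Section 9.1.2 ties that to missing values or discontinuation of study drug, not to interruption. SAP Section 11.1 records that the primary analysis and Period 1 reporting are complete.

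**Conclusion.** The point holds as a contradiction between stated restart rules when both triggers are met, not as an impossible instruction. It runs one way: the second bullet says restart while the first withholds. It arises for baselines above ULN or below ULN/1.5, and for none in between.

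The low-baseline disagreement is temporary; in the example with baseline 0.6 it ends at 0.9 mg/dL. The above-ULN disagreement lasts as long as creatinine stays above ULN, which for a subject who settles at baseline has no fixed end under the first bullet.

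The number affected is unknown and probably small. A wide band of baselines is exposed in principle, and a reader might infer that many subjects are affected. But the conflict between bullets needs a confirmed value of at least 2 mg/dL, which from a baseline of 0.6 is more than a threefold rise (2/0.6 = 3.3). The documents give no incidence. The consequence still open is for Period 2 restarts, exposure and discontinuations.

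The cut-points depend on the ULN, which is assumed. The logic holds for any ULN below 2 mg/dL.

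**What to change.** In Table 4 and France Table 5, reconcile the two creatinine bullets with each other and with the Investigator-determination text in Section 5.5.4 and after the tables. State which restart condition governs when both triggers are met, and say explicitly what applies to a subject whose baseline exceeds ULN. State also whether the Investigator's decision after a long interruption overrides the table. The sponsor's medical team decides the clinical rule; this review takes no view on it.

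The cost is a line or two in each table and a cross-reference. It needs no added testing and does not touch the completed Period 1 analyses.
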